6.4 Schedule of Evaluations for Subjects On-Study, Off-Medications

6.4.1 At any point, subjects may elect to stop study medications but remain on study. Subjects that stay on study but stop medications will not be allowed to resume again.

Subjects will follow the same schedule as defined in Section 6.1 until the end of study. Study medications will not be dispensed at clinic visits, and evaluations related to counseling or monitoring of medications (including urine dipstick and serum creatinine) will not be performed. These include Adherence and Risk-reduction counseling and collection of dried blood spots. If the subject was randomized to the iTab arm, their account will be switched to “inactive.”

STI and HIV rapid test screenings and questionnaires will still be administered as the schedule dictates.

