SOP	standard operating procedure
TDF	tenofovir disoproxil fumarate (Viread)
ULN	upper limit of normal
WBC	white blood cell count
WHO	World Health Organization

SCHEMA

CCTG 595 Vitamin D Sub-study

Effect of Vitamin D Supplementation on Bone Turnover Markers during Tenofovir-Emtricitibine Pre-Exposure Prophylaxis in Men Who have Sex with Men

DESIGN	
CCTG 595 is an open-label clinical trial of the effect of text messaging intervention vs. standard of care on adherence to Truvada (tenofovir-emtricitibine) as PrEP in MSM at increased risk of HIV infection.
 
This sub-study is a matched case-control study, in which cases prospectively take vitamin D3 4000 IU/day beginning at week 24 of PrEP.

DURATION	Subjects will be followed for 6 months (24 weeks)
SAMPLE SIZE	50 eligible subjects will receive vitamin D and will be compared to 50 matched control subjects from CCTG 595 who are not participating in this sub-study.
POPULATION	HIV-negative men aged ≥ 18 years initiating CCTG 595, who are not taking bisphosphonates and do not have a history of osteoporosis, fragility fracture, or kidney stones, or use of tenofovir prior to entry into CCTG 595
REGIMEN	Vitamin D3 4000 IU/day from week 24 through 48 of PrEP with Truvada
ENDPOINTS	Primary endpoint will be changes in bone turnover markers from week 24 through week 48 in the vitamin D intervention group as compared to age- and BMI-matched controls
ANALYSIS	A sample size of 44 subjects per group will provide 80% power to detect a 20% change in P1NP means from week 24 through week 48 between matched cases and controls using a paired t-test with a two-sided $\alpha = 0.05$. To account for attrition, a sample size of 100 is proposed, including 50 vitamin D treated cases and 50 matched controls from CCTG 595.

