8.0 CRITERIA FOR DISCONTINUATION

8.1 Permanent Treatment Discontinuation

- Drug-related toxicity
- Requirement for prohibited concomitant medications
- Subject develops a kidney stone (see section 7.3.1).
- Completion of treatment as defined in the protocol.
- Request by subject to discontinue treatment.
- Discontinuation of PrEP for any reason
- Clinical reasons believed serious by the physician, even if not addressed in the toxicity section of the protocol.

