9.2 Analyses

All analyses are ITT, unless specified otherwise. Evaluable subjects will be individuals who agree to participate in the vitamin D substudy. The primary endpoint analysis will use a paired t-test to compare the changes in P1NP levels from week 24 to 48 weeks between cases and matched controls. Secondary endpoint analyses will include comparison of changes in 25-OH vitamin D levels, PTH, and CTX and will be analyzed analogously to the primary endpoint. If parametric assumptions fail, the corresponding non-parametric test will be applied, in this case, the Wilcoxon signed rank test. Sensitivity analyses will include linear regression models that adjust for possible confounding covariates, such as dietary intake.

Matching: Concurrent controls who are not enrolled in the vitamin D substudy who are reporting supplementation with ≤ 400 IU of vitamin D/day will be matched 1:1 by randomization arm in the CCTG 595 main study (text messaging arm vs. standard of care), age (± 5 years), race/ethnicity, season of study entry, and BMI (± 3 kg/m²).

REFERENCES

1. DHHS Panel on Antiretroviral Guidelines for Adults and Adolescents. Guidelines for the use of antiretroviral agents in HIV-1-infected adults and adolescents. 2014; <http://www.aidsinfo.nih.gov/ContentFiles/AdultandAdolescentGL.pdf>. Accessed May 1, 2014.

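### The vitamin D sub-study does not require a matched control to be on TDF/FTC at week 24, as every case is, so the week 24–48 P1NP contrast may be biased

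*Protocol*

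**What the plan says.** **Cases.** The sub-study schema says that "cases prospectively take vitamin D3 4000 IU/day beginning at week 24 of PrEP", and gives the regimen as "Vitamin D3 4000 IU/day from week 24 through 48 of PrEP with Truvada". Sub-study section 8.1 lists "Discontinuation of PrEP for any reason" among the reasons for stopping vitamin D permanently. A case is therefore on TDF/FTC when the comparison period opens.

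**Controls.** The schema describes them as "50 matched control subjects from CCTG 595 who are not participating in this sub-study". The matching paragraph of sub-study section 9.2 defines them as "Concurrent controls who are not enrolled in the vitamin D substudy who are reporting supplementation with" at most 400 IU of vitamin D per day. It says that controls "will be matched 1:1 by randomization arm in the CCTG 595 main study", age, race/ethnicity, season of study entry and BMI. Current use of TDF/FTC is neither an eligibility condition nor a matching factor. It is not in the exclusion list in sub-study section 4.2 either.

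**Stopping drug in the main study.** Protocol section 6.4 states: "At any point, subjects may elect to stop study medications but remain on study". These participants keep the section 6.1 schedule and may not restart. Of the evaluations that are dropped, section 6.4 says: "These include Adherence and Risk-reduction counseling and collection of dried blood spots". Urine dipstick and serum creatinine are dropped too. Stored plasma is not mentioned. Section 6.3.11 lists stored plasma at day 0 and all visits, and sub-study section 3.0 takes P1NP from that plasma at entry, week 24 and week 48.

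**Analysis.** Sub-study section 9.2 specifies an ITT paired t-test of the week 24 to 48 change in P1NP. Covariate adjustment appears only as a sensitivity analysis, with dietary intake as the one example. The SAP does not cover the sub-study.

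**The concern.** The sub-study hypothesis is that vitamin D blunts the rise in bone turnover markers that follows starting Truvada. The right comparator is a man on tenofovir without vitamin D. The sample-size argument uses that comparator: it assumes that P1NP rises by 20% in unsupplemented controls. A control who stopped TDF/FTC before week 24 does not represent it.

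If such men enter the control group, the control change is pulled down for a reason unrelated to vitamin D, and cases have no matching group at week 24. This shifts the expected value of the primary contrast as well as widening its error. If vitamin D works, the benefit looks smaller. If it does nothing, vitamin D could look mildly harmful.

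**Working it through.** **1. Can an off-drug control arise under the written rules?** Take a participant who stops TDF/FTC at week 8.
- Section 6.4 lets him stay on study on the same schedule.
- Section 6.3.11 lists plasma storage at all visits, so he would have week 24 and week 48 samples if that instruction is followed.
- Sub-study section 9.2 then asks only that he is outside the sub-study, takes no more than 400 IU/day of vitamin D and matches on five factors. He can qualify.
- Applying the section 4.2 exclusions to controls would not remove him.

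The uncertain step is the second, because section 6.4 does not say explicitly that plasma continues off drug.

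**2. The plan's own figure.** Sub-study section 9.1 gives 44 cases and 44 controls for 80% power, two-sided alpha 0.05 and SD of change 40. It mentions an effect of about 24 points from the earlier HIV-treatment trial, and a 20-point difference (controls +20%, cases without that rise). No within-pair correlation is given.
- Unpaired normal formula, n = 2 × [40 × (1.960 + 0.842) / d]². With d = 24, n = 43.6, so 44 per group. With d = 20, n = 62.8, so 63 per group.
- Paired, d = 20: 44 pairs give 80% power if the SD of the pair difference is 46.3, that is 40 × √(2 × (1 − 0.33)). The correlation of 0.33 is back-solved and is an assumption.

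**3. Dilution.** Let f be the share of controls off drug before week 24, and c the P1NP change in those controls minus the change in cases. The expected difference is (1 − f) × 20 + f × c. With flat P1NP in off-drug controls, c = 0:
- f = 10%: 0.9 × 20 = 18 points
- f = 20%: 0.8 × 20 = 16 points

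**4. Power with 44 pairs (noncentral t, two-sided 0.05).**

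| SD of pair difference | 20 points | 18 points | 16 points |
|---|---|---|---|
| 46.3 (reproduces 80%) | 80% | 71% | 61% |
| 47.3 (correlation 0.3) | 78% | 69% | 59% |
| 40 (40 read as the pair-difference SD) | 90% | 83% | 74% |
| 56.6 (no correlation) | 63% | 54% | 45% |

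The starting power depends on the SD. The loss from 20 to 16 points is 16 to 19 percentage points in every row.

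**5. If vitamin D has no effect.** Cases and on-drug controls both rise by 20. Flat off-drug controls at f = 20% make the control mean 0.8 × 20 = 16, a spurious 4-point gap against vitamin D. The chance of p < 0.05 becomes 7–10% over SDs of 56.6 to 40, against the nominal 5%.

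**The case against.** **Plasma may not be drawn off drug.** Section 6.4 drops evaluations tied to counseling or monitoring of medication, and its list of examples need not be complete. What it says will continue is STI tests, rapid HIV tests and questionnaires. Sections 6.2.3 and 3.3 present follow-up plasma as an FTC adherence measure, and section 9.6.3 treats an FTC value as missing after TDF/FTC discontinuation. If plasma is not drawn, an early stopper has no week 24 or week 48 P1NP and cannot be a control. This stands as a real doubt. However, section 9.6.3 is an imputation rule for drug levels, not an instruction to stop storing plasma, and section 6.3.11 makes no exception for men off drug.

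**Size and direction are assumed.** Sub-study section 9.1 says that data on TDF and P1NP without HIV infection are not available, and the documents give no off-drug rate. This also stands. The figures above are illustrations.

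**Stopping after week 24 happens in both groups.** Cases who stop PrEP stop vitamin D but stay in the ITT analysis. That is correct, and the asymmetry is confined to status at week 24.

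**Stronger readings.** A reader might infer that controls need never have taken PrEP. They must have started it, because all CCTG 595 participants begin TDF/FTC at baseline. A reader might also take a much larger loss as the likely one: with 20% of controls off drug and falling by 20%, the difference is 0.8 × 20 − 0.2 × 20 = 12 points and power is 39%. That needs P1NP to be still falling after week 24. It fits men who stop near or after week 24 better than a man who stopped at week 8, and a week 24 rule would largely keep the later stoppers.

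**Intent and scale.** The sub-study title refers to PrEP in progress, so on-drug controls were probably intended, and the open-ended sensitivity regressions could include PrEP status. No operative rule says either. This is a pilot sub-study, and the main trial's comparison is unaffected.

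**Conclusion.** The point holds as a gap in control eligibility. Cases are on TDF/FTC at week 24 by design, and controls are not required to be. The rule as written may therefore admit controls without the tenofovir exposure that the hypothesis and the sample size presuppose. The primary contrast may be biased; the documents do not show that it will be.

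Under the plan's premise that P1NP rises on TDF, the direction is toward hiding a vitamin D benefit. The illustrated loss of power, from about 80% to 71–61%, rests on four assumptions: plasma continues to be stored off drug, 10–20% of controls were off drug before week 24, their P1NP is flat from week 24 to 48, and the pair-difference SD is 46.3. The documents supply neither the off-drug share nor the P1NP change.

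**What to change.** - **Matching rule (sub-study section 9.2).** Add that a control must be on TDF/FTC at week 24, shown by dispensing at that visit and no TDF/FTC discontinuation CRF dated on or before it. This is the state a case is in when vitamin D starts. It uses only information available at the start of the comparison period.
- **Primary analysis.** Keep cases and controls who stop TDF/FTC after week 24 in the ITT comparison, and say so.
- **Sensitivity analysis.** Repeat the paired comparison in pairs where both members have FTC detected in stored plasma at weeks 24 and 48. Name the cut-off: protocol section 10.1 uses 1 ng/mL, and the SAP's FTC endpoint uses 0.35 ug/ml.
- **Section 6.4.** State whether stored plasma continues off drug.

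The rule uses records that the main study already collects, and the planned 44 pairs (50 with attrition) do not change. The cost is a somewhat smaller pool of matchable controls. At most 400 − 50 = 350 participants are outside the case group. The requirements for concurrency, the 400 IU/day limit and matching on five factors reduce that number before the new condition applies.

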Appendix V: Multivitamin Supplement Comparisons

	Multivitamin Supplement					
	Calcium and Vitamin D content					
References	Drug Facts and Comparisons					
	Dietary Supplements Database (http://dietarysupplements.nlm.nih.gov)					
Manufacturer/ Brand	Product	servings	Calcium/ serving (mg)	VitD/serving (IU)		
21st Century	Multi Vitamin and Multi Mineral Diabetes formula	3 tablets	1500	400.00		
4Life	CM Super Calcium & Magnesium Superiority	3 tablets	2000	400.00		
	Multiplex Vitamin & Mineral Formula	2 tablets	100	400.00		
	RiteStart Men	2 tablets	225	400.00		
	RiteStart Women	2 tablets	1100	400.00		
	Transfer Factor	2 tablets	200	400.00		
Alacer	Emergen C Immune Defense Drink Mix	1 packet	50	100.00		
	EmerGen-C Kids Multi (various flavors)	1 packet	63	400.00		
Albertsons	Calcium + D	2 tablets	1200	400.00		
Alcon	I Caps MV Major	4 tablets	330	400.00		
American Health	Chewy Bears Multi Vitamin with Calcium 250mg	2 bars	250	400.00		
	More Than a Multiple (with or without iron)	3 tablets	500	400.00		
	Nutri-Mega	2 capsules	400	400.00		
Amerifit	Estoven Plus Multi-Vitamin	1 capsule	200	1000.00		
	Estroven PM	1 capsule	60	800.00		
	Estroven Maximum Strength	1 capsule	100	400.00		
AmeriScience s	Childrens Chewable	1 tablet	20	400.00		
	Mens Master-Multi	2 packets	540	400.00		
	Osteo	1 tablet	175	300.00		
	Sleep	4 tablets	250	150.00		
	Womens Master-Multi	1 packet	585	400.00		

AN	Active Womans Formula	3 tablets	400	400.00		
	Prenatal Plus	4 tablets	800	400.00		
Anselmo	Super Multis	3 tablets	105	800.00		
Atkins	Basic 3	3 tablets	50	200.00		
	Barefoot Coral Calcium Plus	3 tablets	250	400.00		
Azur Pharm	Natalle-ez	1 tablet	100	400.00		RX only
Bayer	Citracal Plus Bone Density Builder	2 tablets	600	400.00		
	Citracal Plus Heart Health	1 tablet	315	250.00		
	Citracal UltraDense Calcium Citrate Petites	2 caplets	630	400.00		
	Citracal UltraDense Calcium Citrate Tablets	2 tablets	400	400.00		
	Citracal UltraDense Calcium Citrate Plus with Magnesium	2 tablets	500	250.00		
Belvedere	Healthy Day Multi	1 tablet	100	400.00		
	One a Day	1 tablet	20	200.00		
Bionatures	Advanced Mega Multi	6 capsules	400	400.00		
	Bone Support	3 capsules	500	200.00		
	Coral Calcium Plus - 1000mg	1 tablet	715	200.00		
Biotics	Aqueous Multi-Plus	1 tablet	25	400.00		
	Bio-Multi Plus (all types)	3 tablets	200	400.00		
BodyTech	Tech X Lite	1 packet	300	240.00		
	Tech X Mass Gainer	1 packet	500	200.00		
Breckenridge	Multifol Tablets	1 tablet	125	400.00		
	Vinate GT	1 tablet	200	400.00		RX only
	Vinate II	1 tablet	200	400.00		RX only
	Vinate-M	1 tablet	200	400.00		RX only
	Vinate Calcium	1 tablet	125	400.00		RX only
	Multifol Plus	1 tablet	100	400.00		RX only
Bronson Laboratories	Calcium 600mg with Vitamin D	4 tablets	125	500.00		
	Therapeutic Vitamin & Mineral Formula	1 tablet	100	400.00		

Brookstone	BP Prenate	1 tablet	100	425.00	RX only
Canopy Roads Pharmaceuticals	CRNatal	1 tablet	100	425.00	RX only
Carlson	Cardi-Rite	4 tablets	400	400.00	
	Kids Chewable Vitamins with Minerals	1 tablet	50	400.00	
	Liquid Cal Mag	1 gelcap	200	500.00	
	Mini-Gel Vitamins & Minerals	6 gelcaps	1000	1200.00	
	Mini-Multi Vitamins & Minerals	1 tablet	20	400.00	
	Super-1-Daily Vitamins & Minerals	1 tablet	50	400.00	
	Super-2-Daily Vitamins & Minerals	2 tablets	50	600.00	
Centrum	Regular	1 tablet	200	400.00	
	Performance	1 tablet	100	400.00	
	Silver	1 tablet	200	400.00	
	Women's Silver	1 tablet	500	800.00	
	Men's Silver	1 tablet	250	600.00	
	Chewable	1 tablet	108	400.00	
	Cardio	1 tablet	54	200.00	
	Advanced	1 tablet	162	400.00	
	Ultra Men's Formula	1 tablet	210	600.00	
	Ultra Women's Formula	1 tablet	500	800.00	
	Kids Complete Chewable (various)	1 tablet	108	400.00	
Country Life	Chewable Adult Multi	8 wafers	480	400.00	
	Daily Total One	2 wafers	40	400.00	
	Life Essential Lfe Caps	8 caps	320	400.00	
	Max for Men	4 tablets	200	400.00	
	Daily Multi Sorb	2 tablets	50	400.00	
	Liquid Multi	30ml	50	400.00	
	Life Superior Multiple	3 wafers	200	100.00	
Cyclin	VITa-PMS Plus	1 tablet	167	17.00	
Cypress	Calcium 600 with D	1 tablet	600	200.00	
	Calvite P & D	1 tablet		120.00	
	Prenatal AD	1 tablet	200	400.00	RX only
	Prenatabs CBF	1 tablet	200	400.00	RX only
	Prenatab FA	1 tablet	200	400.00	RX only
	Prenatal 19 (Regular & Chewable)	1 tablet	200	400.00	RX only
	Prenatabs OBN	1 tablet	200	400.00	RX only
	Trinate	1 tablet	200	400.00	RX

					only
	PrenaFirst	1 tablet	200	400.00	RX only
Cytosport	Cytogainer (all flavors)	6 scoops	500	200.00	
	Muscle Milk (all flavors)	240ml	1000	600.00	
Douglas Labs	FM Support Pack	1 packet	250	50.00	
	Pro-PCA Fuel	4 scoops	250	200.00	
	Ultra-Ostivone	4 capsules	600	200.00	
ETHEX	NutriSpire Tablets	1 tablet	200	400.00	
	Prenatal MR 90 FE	1 tablet	250	400.00	RX only
	NatalCare PIC Forte	1 tablet	250	400.00	RX only
	Advanced NatalCare	1 tablet	200	400.00	RX only
	Ultra NatalCare	1 tablet	200	400.00	RX only
	NatalCare GlossTabs	1 tablet	200	400.00	RX only
	Advanced-RF NatalCare	1 tablet	200	400.00	RX only
	Prenatal Z Advance formula	1 tablet	200	400.00	RX only
	Prenatal RX 1	1 tablet	200	400.00	RX only
	NataTab CFe	1 tablet	200	400.00	RX only
	NataTab FA	1 tablet	200	400.00	RX only
	CareNatal DHA	1 tablet	200	400.00	RX only
	NatalCare Three	1 tablet	200	400.00	RX only
	Prenatal MTR with Selenium	1 tablet	200	400.00	RX only
	NatalCare Plus	1 tablet	200	400.00	RX only
	NatalCare PIC	1 tablet	125	400.00	RX only
	Cal-Nate	1 tablet	125	400.00	RX only
	NatalCare RX	1 tablet	100	200.00	RX only
Everett	Vitafol Caplets	1 caplet	125	400.00	
	Vitafol-PN Caplets	1 caplet	125	400.00	
	Vitafol-OB Caplets	1 caplet	125	400.00	
	Calcifolic-D Wafers	1 wafer	125	300.00	
	Vitafol-OB+DHA	1 tablet	100	400.00	Rx

Freeda	Yelets Teenage Formula	1 tablet	60	400.00		
	Monocaps	1 tablet	50	400.00		
	Vitalets Chewables	1 tablet	80	200.00		
	Quintabs-M	1 tablet	30	400.00		
	Ultra-Freeda with Iron	1 tablet	83	133.00		
	Ultra-Freeda	1 tablet	83	133.00		
	Fem-Cal	1 tablet	80	100.00		
	Fem-Cal Citrate	1 tablet	60	80.00		
	KPN Prenatal with Extra Calcium	1 tablet	333	133.00		
	A-Free Prenatal	1 tablet	333	133.00		
Future Biotics	Calcium Essentials	6 caps	900	100.00		
	Hair Skin and Nails	6 tablets	1200	400.00		
	MV Teen	3 capsules	100	400.00		
	PMSharmony	8 tablets	600	200.00		
	Pressure Lo	4 tablets	1000	300.00		
	Vegetarian Super Multi	6 tablets	400	400.00		
	Vitomegamen	3 tablets	100	400.00		
	Vitomegawomen	3 tablets	100	400.00		
GNC	ActiveCal	2 tablets	1000	200.00		
	Calcimate Plus 800mg	4 caps	800	800.00		
	Calcium Citrate Plus 800	2 caps	400	400.00		
	Chewable Calcium 600	1 tablet	600	200.00		
	Coral Calcium	4 capsules	800	400.00		
	Kids Multibite Plus minerals Chewable	2 tablets	30	400.00		
	Kids Vitamin Chews	1 tablet	150	400.00		
	Mega Men Sport	4 capsules	400	400.00		
	Mega Teen	3 tablets	100	400.00		
	Mens Mega Men	4 tablets	400	400.00		
	Mens Mega Men 50 PLUS	2 capsules	200	400.00		
	Men's Mega Multi Time Release	2 tablets	200	1600.00		
	Multi Mega Minerals	2 tablets	1000	400.00		
	Multi-Gel	2 gelcaps	200	400.00		
	Natural Brand Fantastic Fiber	10gm	250	400.00		
	Preventron	4 tablets	60	400.00		
	Solotron (with or without)	1 tablet	60	400.00		
	Solotron Platinum	2 tablets	200	400.00		
	Teen Chewable Mega Teen	2 tablets	100	400.00		
	Ultra Mega Gold (with or without iron)	2 tablets	100	400.00		
	Ultra Mega Green	2 capsules	50	400.00		
	Ultra Mega Timed Release	2 tablets	100	400.00		
	Ultra Mega Two Timed Release (with or without iron)	2 tablets	50	400.00		
	Women's Mega Multi Time Release	2 tablets	200	1600.00		

	Women's Prenatal without Iron	2 tablets	500	400.00		
	Womens Ultra Mega	2 capsules	500	400.00		
Garden of Life	Living Calcium Advanced	3 capsules	500	300.00		
	Living Multi Optimal Womens formula	6 capsules	400	200.00		
	Vitamin Code 50 & Wiser Women	4 capsules	50	1000.00		
	Vitamin Code Men	4 capsules	20	400.00		
GlaxoSmithKline	Geritol Complete	1 tablet	148	400.00		
	Fiber Choice Chewable	1 tablet	100	50.00		
	Os-Cal Ultra	1 caplet	600	500.00		
	Os-Cal Chewable	1 caplet	500	600.00		
	Oscal-D	1 caplet	500	200.00		
	Oscal Extra D	1 caplet	500	600.00		
	Oscal 500 + D	1 tablet or 1 chewable	500	400.00		
Goldline	Therapeutic Tablets	1 tablet	400	400.00		
	Calc carb 600 with Vitmain D	1 tablet	600	200.00		
	Oyst-Cal-D	1 tablet	200	125.00		
	Health HNS Fat Cutter	4 tabs	600	400.00		
	Healthy N Fit Nutri Pack	1 tablet	1000	400.00		
Hawthorne	ICAR Prenatal Therapy	1 tablet	600	200.00		RX only
Health Sense	Once Daily	1 tablet	400	400.00		
	Complete Senior	1 tablet	200	400.00		
Hero Nutritionals	Vegetarian Calcium with Vitamin D	1 gummie	125	100.00		
Integrative Therapeutics	Vitaline Total Formula 3	1 tablet	500	400.00		
Integrity	Stuart Prenatal	1 tablet	200	400.00		RX only
Irwin Naturals	Kids Supervitamin	1 softchew	150	400.00		
	Super Calcium	3 capsules	1000	400.00		

	Mens Living Green Lig-Gel Multi	3 gelcaps	50	400.00		
	Liqui-Gel Multi	4 capsules	100	200.00		
Ivax	Certagen Tablets	1 tablet	162	400.00		
	One-Tablet-Daily with Minerals	1 tablet	162	400.00		
	Generix-T	1 tablet	58	400.00		
	Prenatal S	1 tablet	200	400.00		
Jarrow Formulas	All Capsule Health Pak	1 packet	500	200.00		
	Bone-Up	6 capsules	1000	400.00		
KAL	Enhanced energy	3 tablets	300	400.00		
	Amino-Max	2 tablets	1000	200.00		
	Beyond Calcium Ipriflavone	5 tablets	1000	400.00		
	Bone Meal	4 tablets	1000	400.00		
	Cal Citrate Plus	4 tablets	1000	400.00		
	Enhanced Energy Teen Complete	1 tablet	100	400.00		
	High Potency Soft Multiple	2 capsules	200	400.00		
	Mega Vita-Min	1 tablet	50	400.00		
	Multi-Four Plus	4 tablets	500	400.00		
	Multi-Max 1	1 tablet	50	400.00		
	Multiple Energy	4 tablets	500	400.00		
	MultiSaurus DinoSours	1 packet	50	200.00		
	Vita Mom Advanced	3 tablets	600	200.00		
Kenwood/Bradley	Kenwood Therapeutic Liquid	5ml	250	133.00		
Kirkland Signature	Calcium 500mg + D	2 tablets	1000	400.00		
	Calcium Chews 500mg + D + K	2 chews	1000	400.00		
	Calcium Citrate, vitamin D, Magnesium & Zinc	2 tablets	500	250.00		
	Childrens Chewable Multivitamin	1 tablet	200	400.00		
	Daily Multivitamin Pack with Energy Boosting Nutrients	1 pack	1200	400.00		
	Daily Multivitamin with Lutein	1 tablet	162	400.00		
	Mature Multi Vitamins & Minerals	1 tablet	200	400.00		
	Premium Performance Multivitamin with Lycopene & Lutein	1 tablet	165	400.00		
Laser	Lactocal-F	1 tablet	200	400.00		RX only
Leiner	One Daily Mens Health Formula	1 tablet	210	400.00		

Life Enhancements	3-way Calcium complex (Womens Health)	2 capsules	500	400.00		
	BioEnhance with DNABLE	4 capsules	1000	50.00		
Life Extension	Childrens Formula Life Extension Mix	2 tablets	100	400.00		
	Mix with Extra Niacin Without Copper	4 tablets	100	400.00		
	LifePlus Daily Biobasics	1 scoop	500	300.00		
	Liquimins Ca; Mag Zinc	1.25ml	1200	400.00		
	Longs Womnes Multivitamin/Multimineral.Herbs	2 tablets	500	400.00		
	MD Select Advanced Breast support	2 capsules	225	400.00		
Major	Certavite with Lutein	1 tablet	162	400.00		
	Certavite with Lutein	1 tablet	160	400.00		
	High Potency	1 tablet	60	400.00		
	Thera	1 tablet	400	400.00		
	Calcium 600-D	1 tablet	600	200.00		
	Oyster Shell Calcium 500 + D	1 tablet	500	200.00		
	Oyster Shell Calcium with D	1 tablet	400	125.00		
	Prenatal Plus	1 tablet	200	400.00		
Marmel	Marnatal-F Plus	1 tablet	250	400.00		RX only
McNeil	Viactiv	1 caplet	200	400.00		
	Viactiv for Teens	1 tablet	500	200.00		
	Viactiv Calcium plus Vitamin D and K	1 chew	500	100.00		
	Viactiv Flavor Glides	1 glide	500	100.00		
	Viactiv Multi Vitamin Flavor Glides	1 glide	200	400.00		
	Viactiv Multivitamin Chocolate Milk	8oz	200	400.00		
Michaels Neuropathic	Childrens Chewables	4 wafers	200	400.00		
	JUST ONE Multivitamin	1 tablet	50	400.00		
	Vision Factors	6 tablets	150	100.00		
Miller	Ragus	1 tablet	193	133.00		
	Complexe	1 tablet	150	133.00		
	Sclerex	1 tablet	8	67.00		

	Theramill Plus	1 tablet	67	33.00	
	Theramill Forte	1 capsule	67	33.00	
Mission	Calcet Plus	1 tablet	160	400.00	
	Fosfree	1 tablet	175	150.00	
	Citracal	1 caplet	315	200.00	
	Citracal Plus	1 caplet	300	125.00	
	Calcet	1 tablet	200	100.00	
	Citracal Prenatal 90 + DHA	1 tablet	200	400.00	RX only
	CitraNatal 90 DHA	1 tablet	200	400.00	RX only
	Citracal Prenatal + DHA	1 tablet	125	400.00	RX only
	CitraNatal DHA	1 tablet	125	400.00	RX only
	CitraNatal Rx	1 tablet	125	400.00	RX only
	Prenatal F.A	1 tablet	50	400.00	
	Prenatal HP	1 tablet	50	400.00	
	Prenatal	1 tablet	50	400.00	
Natrol	My Favorite Multiple	4 tablets	200	400.00	
	My Favorite Multiple with Coral Calcium and Zeaxanthin	2 capsules	250	400.00	
Naturade	Head Start Nutritional Breakfast drink	240ml	200	100.00	
	Power Shake	1 scoop	280	400.00	
	Ribo-tein Vital	1 scoop	280	400.00	
	Super Weight Gain	4 scoops	30	200.00	
Natural Factors	Big Friends Childrens Chewable (various flavors)	1 tablet	65	400.00	
	Calcium & Magnesium Citrate with D	4 tablets	1000	400.00	
	Mens 50 Plus MultiStart	4 tablets	400	200.00	
	Mens MultiStart	4 tablets	400	100.00	
	MultFactors Womens 50 Plus	3 Capsules	200	1000.00	
	MultiStart prenatal	3 capsules	500	50.00	
	Super Multi Iron Free	1 tablet	125	400.00	
	Ultra Multi Plus	1 tablet	125	400.00	
	Womens MultiStart	3 tablets	500	200.00	
	Womens Plus MultiStart	3 tablets	500	200.00	
Nature Made	Women's Multi for Her	1 tablet	250	1000.00	
	Men's Multi for Him	1 tablet	162	1000.00	
	Women's Multi for Her 50+	1 tablet	250	1000.00	
	Men's Multi for Him 50+	1 tablet	162	1000.00	
	Advanced High Absorption Calcium with 100mg Phytonutrients	2 tablets	500	200.00	

	Calcium Magnesium Zinc with Vitamin D	1 tablet	333	200.00		
	Calcium Plus soy	1 tablet	500	200.00		
	Calcium with Vitamin D	1 tablet	600	200.00		
	Diabetes Health Pack	1 packet	200	400.00		
	Essential 50+	1 tablet	200	400.00		
	Essential Balance Compete Multi Vitamin/Mineral	1 tablet	100	400.00		
	Essentail Daily	1 tablet	450	400.00		
	Essential Man 50+	1 tablet	450	400.00		
	Essential multi Plus Energy	1 tablet	50	200.00		
	Essential Woman 50+	1 tablet	250	400.00		
	Man with Lycopene	1 tablet	100	400.00		
	Maximin Pack	1 packet	850	800.00		
	Mens Pack	1 packet	350	400.00		
	Multi Complete with Iron & Calcium	1 softgel	100	1000.00		
	Multi for Her with Iron & Calcium	1 softgel	100	1000.00		
	Multi Prenatal Premium	1 tablet	200	400.00		
NatureSmart	Disney Princess Complete Multivitamin Chewable Tablet	1 tablet	100	400.00		
	Winnie the Pooh Chewables	1 tablet	100	400.00		
	Gummies (Finding Nemo, Winnie the Pooh, etc)	1 gummies	100	400.00		
Natures Best	Hardcore Pack	1 packet	1100	400.00		
	Zero Carb Isopure	1 scoop	300	100.00		
Nature's Bounty	Theravim-M	1 tablet	40	400.00		
	Multi-Day plus Minerals	1 tablet	162	400.00		
	Mega VM-80	1 tablet	19	400.00		
	Absorbable Calcium 1220 + D	2 softgels	1200	200.00		
	Calcium 500mg with Vitamin D	4 tablets	120	500.00		
	Calcium 600 + Vitamin D with Soy Isoflavones	2 tablets	100	400.00		
	Chewable Calcium Wafers Plus Vitamin D	2 wafers	200	200.00		
	Coral Calcium 1000mg Plus Vitamin D and Magnesium	2 tablets	370	400.00		
	Green Source	3 tablets	250	400.00		
	Hair Skin and Nails Formula	3 tablets	830	100.00		
	High Potency Vitamin D 1000IU	1 tablet	120	1000.00		
	Multi-Day Weight Trim with Green Tea EGCG	1 tablet	300	400.00		
	Oystercal-D Calcium 500mg with Vitamin D3	1 tablet	500	400.00		
	Pre-Natal Formula	1 tablet	200	400.00		
	Prescriptive Formulas Optimal Mens	1 packet	712	200.00		
	Prescriptive Formulas Optimal Womens	1 packet	975	525.00		

	Soy Protein shake Powder	30gm	900	40.00		
	Ultra Man Time Release	2 tablets	200	200.00		
	Ultra Vita-Min	1 tablet	60	400.00		
	Ultra Woman	2 tablets	500	400.00		
	Vitmain D 2000IU	1 tablet	1500	2000.00		
Natures Life	Antioxidant Soft Multi	2 softgels	200	400.00		
	Great Greens	3 tablets	250	800.00		
	Green Pro-96 Multi	1 tablet	50	200.00		
	One Daily Vegetarian Multiple	1 capsule	20	400.00		
	Prenatal Multiple	6 capsules	1000	200.00		
	Soft Gelatin Multiple	2 softgels	200	400.00		
	Stress Soft Multi	2 softgels	200	400.00		
	Ultra Mega Vite Multi	1 tablet	100	400.00		
Natures Plus	Adults Chewable MultiVitamin and Minerals	1 tablet	10	400.00		
	Adults Chewable Vitamin D3 1000IU	1 tablet	80	1000.00		
	Adults Dental Care Probiotic Lozenges	1 lozenges	150	400.00		
	Adults Multi-Vitamin Chewable	1 tablet	10	400.00		
	Childrens Chewable Dental Probiotic (various flavors)	2 tablets	300	400.00		
	Bone Power - Calcium with Boron	4 softgels	1000	200.00		
	Dyno Vites Sustained Release	2 tablets	50	1000.00		
	Golden Years	6 tablets	300	400.00		
	Especially Yours Women's Multiple	3 tablets	150	400.00		
	Liquid Bone Power	15ml	1000	200.00		
	Liquid Calcium	15ml	1000	40.00		
	Love Bites Childrens Chewable	1 tablet	20	400.00		
	Mega Force Tablets for Men Only	3 tablets	25	400.00		
	Nutri-Genic Softgels for Sensitive People	2 softgels	50	400.00		
	Nutri-Genic Tablets for Sensitive People	2 tablets	50	400.00		
	Power Teen for Her Chewable	2 tablets	100	500.00		
	Power Teen for Him Chewable	2 tablets	50	500.00		
	Power-Plex sustained release MultiVitamin and Mineral	1 tablet	26	400.00		
	Regeneration Liquid Sunshine	60ml	200	400.00		
	Regeneration Multivitamin and mineral Softgels	3 softgels	100	400.00		
	Source of Life Adults Chewable Multi	2 wafers	100	400.00		
	Source of Life Animal Parade Liquid	30ml	20	200.00		
	Source of Life GOLD Mini-Tablets	3 tablets	250	400.00		
	Source of Life Gold tablets	3 tablets	250	400.00		
	Source of Life Gold Vcaps (Vegan)	9 caps	250	1000.00		
Natures Secret	womens Whole Body Daily Multivitamin	2 softgels	100	400.00		

Natures Sunshine	Super Supplemental Vitamins and Minerals without Iron	4 tablets	400	600.00		
Natures Way	Alice Iron-Free Multivitamin	3 tablets	250	400.00		
	Alive Mens Multivitamin & Mineral	3 tablets	250	800.00		
	Alive Womens Multivitamin & Mineral	3 tablets	500	1000.00		
	BoneSoy	2 tablets	400	133.00		
	Coral Calcium	3 capsules	600	200.00		
	Natures Way Alive	3 tablets	250	400.00		
	Once Daily Women's 50 +Ultra Potency	1 tablet	500	1000.00		
	Once Daily Men's 50 +Ultra Potency	1 tablet	100	1000.00		
	Alive Once Daily Energy 50 +	1 tablet	100	1000.00		
New Chapter	Every Womans Daily	1 tablet	10	400.00		
	Bone Strength Take Care	3 tablets	680	800.00		
	Every Man	3 tablets	8	400.00		
	Every Woman	3 tablets	25	400.00		
	Every Woman II	6 tablets	75	400.00		
	Only One	1 tablet	2	400.00		
	Perfect Prenatal	3 tablets	30	400.00		
	Unbound Energy	3 tablets	5	1000.00		
New Phase	Complete Menopause Support	4 capslets	800	400.00		
Nnodum Pharmaceuticals	Inatal Advance	1 tablet	200	400.00		RX only
	Inatal Ultra	1 tablet	200	400.00		RX only
North Star	Daily Defense Plus	3 capsules	200	200.00		
	Ultimate Bionic Plus	1 packet	500	400.00		
Novato	Multivitamin Plus	1 tablet	200	400.00		
	Super Multivitamins	2 capsules	50	400.00		
Now Foods	Full Spectrum Minerals	2 tablets	1000	200.00		
	ADAM Superior	3 capsules	350	400.00		
	Bone Calcium	4 tablets	1000	200.00		
	Daily Vits Vitamin	1 tablet	150	100.00		
	Calcium Citrate	2 tablets	600	100.00		
	Eco-Green Multi Vitamin	2 capsules	50	100.00		
	Full Spectrum Minerals	2 tablets	1000	200.00		
	Kids Vit Chewable (various flavors)	2 tablets	40	200.00		

	Liquid Cal Mag	15ml	500	400.00		
	Liquid Multi Gels	2 gelcaps	100	400.00		
	Magnesium & Calcium	3 tablets	400	200.00		
NSI	Prenatal Plus	6 capsules	1300	400.00		
	Synergy Basic Multi Vitamin Version 2	2 capsules	20	700.00		
	Synergy Mens Multi Vitamin Version 2	8 capsules	50	700.00		
	Synergy Multi Vitamin Version 10	6 capsules	500	1000.00		
Nutrilite	Cal Mag D	4 tablets	1000	400.00		
	Daily Multivitamin and Multiminerals	1 tablet	200	400.00		
Nutrition Now	Calcium Soft Chews	1 softchew	500	100.00		
	Rhino Beanie Vites	2 tablets	4	100.00		
	Rhino Calcium	1 tablet	250	100.00		
	Rhino Wigglers	1 wiggler	2	400.00		
One A Day	Essential Multi	1 tablet	45	400.00		
	Men's Health	1 tablet	210	400.00		
	Men's 50+	1 tablet	120	400.00		
	Women's	1 tablet	450	800.00		
	Maximum	1 tablet	162	400.00		
	Complete Chewable (Flintstones, Bugs Bunny, Scooby Doo, etc)	1 tablet	100	400.00		
	Gummies (Flintstones, Bugs Bunnies, etc)	1 gummie	100	400.00		
	Energy	1 tablet	250	400.00		
	Active	1 tablet	110	400.00		
	Cholesterol Plus	1 tablet	200	400.00		
	Daily Multivitamin Vital Body and Cells Formula	1 tablet	200	400.00		
	Joint and Bone Vitality	1 tablet	250	67.00		
	Men's Pro Edge	1 tablet	200	800.00		
	Menopause Formula	1 tablet	300	800.00		
	Women's Prenatal	1 tablet	300	400.00		
	Women's Active Mind & Body	1 tablet	300	800.00		
	Women's Active Metabolism	1 tablet	300	800.00		
	Weight Smart	1 tablet	300	400.00		
	Carb Smart	1 tablet	200	400.00		
	Today	1 tablet	240	400.00		
	Science Daily	1 tablet	250	400.00		
	Nutrilite	1 tablet	200	400.00		
	Teen Advantage for Her	1 tablet	300	800.00		
	Teen Advantage for Him	1 tablet	200	400.00		
Optimox	Gynovite Plus	1 tablet	83	67.00		

Optimum Nutrition	OptiMen	3 tablets	200	300.00		
	OptiWomen	2 capsules	150	600.00		
	Nutrition Serious Mass	2 scoops	590	200.00		
Perque	Life Guard	2 tablets	50	400.00		
	Bone Guard Forte 20	4 capsules	500	400.00		
	Life Guard Chewables	1 chewable	50	200.00		
	Mito Guard 100 Plus	1 tablet	50	200.00		
Pfizer	Myadec	1 tablet	162	400.00		
	Caltrate 600-D	2 tablets or softchews	1200	800.00		
	Caltrate 600-D Plus minerals	2 tablets or softchews	1200	800.00		
Pharmanex	Bone Formula	2 tablets	250	50.00		
	Life Essentials	1 tablet	100	200.00		
	LifePak Kosher	1 packet	250	200.00		
	LifePak Prenatal	1 packet	325	200.00		
	LifePak Prime Anti Aging Formula	1 packet	500	300.00		
	LifePak Teen	1 capsule	250	200.00		
	LifePak Women	1 packet	500	200.00		
	Nutrimune chews	1 chewtab	250	50.00		
	Vitox	2 capsules	250	200.00		
Pharmaton	Ginsana Gold Formula	2 softgels	200	400.00		
Pharmics	O-Cal FA	1 tablet	200	400.00		RX only
PhysioLogics	MultiLogics Iron-Free Once Daily	1 capsule	92	400.00		
	OsteoLogic Pro	2 tablets	400	150.00		
	Phytototality Daily Multivitamin + Minerals	3 tablets	252	400.00		
	Ultra MultiLogics for Men High Potency	2 tablets	200	400.00		
	Ultra Multilogics for Women High Potency	2 tablets	500	600.00		
Precision Engineered	Milk and Egg Protein Powder	1 scoop	600	140.00		
	Muscle Weight Gainer	5 tbs	1100	200.00		
	ProtoPlex Deluxe	3 scoops	600	200.00		

Prevention	Age-Defying Multivitamin & Mineral for Men 50 Plus	2 tablets	250	400.00		
	Diabetic Support MultiNutrient	2 tablets	240	400.00		
	High Potency Multivitamin & Mineral for Women	1 tablet	250	400.00		
Prime Marketing	Thera-M with Minerals	1 tablet	40	400.00		
	Complete Tablets	1 tablet	162	400.00		
	Prenatal	1 tablet	200	400.00		
Pure Encapsulations	Nutrient 950 (various formulations)	6 capsules	300	800.00		
	PureBears	2 tablets	100	400.00		
	Daily Multi	3 capsules	200	200.00		
Puritans Pride	ABC PLUS SENIOR with Lutein & Lycopene	1 tablet	200	400.00		
	Absorbable Calcium with Vitamin D	2 capsules	1000	100.00		
	Adult Chewable Multi-Vitamin	1 chewtab	10	400.00		
	Calcium Magnesium with D	3 tablets	1000	400.00		
	Childrens Chewable Animal Chews (various formulations)	1 chewtab	125	200.00		
	Childrens Chewable Multivitamin	1 chewtab	50	400.00		
	Complete One	1 tablet	54	400.00		
	Daily 3 Multiple with Cholesterol Regulators	3 capsules	106	800.00		
	Formula 100 with Beta Carotene	1 tableet	100	400.00		
	Green Source	3 tablets	750	400.00		
	High Potency Calcium 600 + Vitamin D	2 tablets	1200	400.00		
	Iron Free green Source	3 tablets	252	400.00		
	Mega Vita Gel	2 softgels	200	400.00		
	Mega Vita Min for Seniors	2 tablets	200	400.00		
	Mega Vita Min for Women	2 tablets	500	400.00		
	Mega Vita min for Women Timed Release	2 tablets	510	400.00		
	Mega Vita Min	1 capsule	15	400.00		
	Multi-Day Plus Minerals	1 tablet	162	400.00		
	Multi-Day Take One Green Tea Formula	1 tablet	300	400.00		
	Potent 75 Super VM	1 tablet	50	400.00		
	Prenatal Complex	4 capsules	1300	400.00		
	Puratron	6 tablets	800	400.00		
	Super All Day Nutricom Powder	15gm	500	400.00		
	Ultra Vita-Mam Time Release for Men	2 tablets	200	200.00		

	Ultra Vita-Min VM-33	1 tablet	60	400.00		
	Vita-min Complete Formula 1	6 tablets	800	200.00		
	Whole Food Concentrate	3 capsules	500	400.00		
Quantum	Mega 1 Daily Iron Free	1 capsule	25	200.00		
	Natures Daily Multi Vitamin	1 tablet	50	400.00		
	Complete Super Vitamin Multi	1 tablet	50	400.00		
Radiance	Absorbable Calcium with Vitamin D	2 softgels	1000	100.00		
	Calcium 600 + Vitamin D	2 tablets	1200	250.00		
	Coral Calcium 500 Plus	2 capsules	370	400.00		
	Green Source Multivitamins and minerals	3 tablets	250	400.00		
	Mega Vita Gel	2 softgels	200	400.00		
	Mega Vita Min for women	2 tablets	500	400.00		
	Mega Vita Min High Potency 9 time Release	2 tablets	500	400.00		
	Prenatal Vitamin	1 tablet	200	400.00		
	Skin, Hair & Nails Formula	3 tablets	834	100.00		
	Ultra Vita Man High Potency Timed Release	2 tablets	200	200.00		
	Vanilla Soy Protein shake	30gm	200	200.00		
